6.7.2 HANDLING OF MISSING DATA IN QUESTIONNAIRE BASED, SELF-REPORTED DATA OUTCOME

For questionnaire-based outcomes, missing data will be handled as *missing at random*. To handle this, 100 multiple imputations will be performed, using following variables: stratification variables: diagnosis, municipality, employment status; age; gender; time to stable RTW; psychometric variables at baseline and all follow-up at outcome time: BDI, BAI, WSAS and PSS.

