6.8.2.7 REPORTING AND STATISTICAL METHODS TO HANDLE MISSING DATA

Same as 6.8.1.7.

6.8.3 ALL SELF-REPORTED, NUMERICAL OUTCOMES, AT 6-, 12-, AND 24-MONTH FOLLOW-UP AT (SECONDARY OUTCOMES ##4-7 AND PREDEFINED EXPLORATORY OUTCOMES ##16-48)

6.8.3.1 CALCULATION OF THE OUTCOME: SPECIFIC MEASUREMENT AND UNITS (AND TRANSFORMATION, WHERE APPLICABLE)

All outcomes are calculated as the sum of scores on the respective measurement scales.

All 6-month follow-up outcome analyses are calculating using baseline and 6-month follow-up observations.

All 12-month follow-up outcome analyses are calculating using baseline and 6- and 12-month follow-up observations.

All 24-month follow-up outcome analyses are calculating using baseline and 6-, 12-, and 24-month follow-up observations.

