6.8.3.2 SPECIFIC ANALYSIS METHOD AND RESULT PRESENTATION

Linear mixed-effects model with unstructured covariance. Results will be presented in pairwise group differences between outcomes, from the estimated marginal means from the model, and the confidence intervals of these differences.

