6.8.3.7 REPORTING AND STATISTICAL METHODS TO HANDLE MISSING DATA

Proportion and amount of missing data per outcome variable per follow-up event per treatment group will be reported.

To handle missing data, 100 multiple imputations will be performed, using following variables: stratification variables: diagnosis, municipality, employment status; age; gender; time to stable RTW; psychometric variables at baseline and all follow-up at outcome time: BDI, BAI, WSAS and PSS.

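### The imputation list omits the own earlier scores of eight exploratory scales, and randomised arm, so the imputation model is poorer than the mixed model it feeds

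*SAP*

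**What the plan says.** SAP 6.7.2 applies to all questionnaire outcomes ("For questionnaire-based outcomes, missing data will be handled as" missing at random) and continues: "To handle this, 100 multiple imputations will be performed, using following variables". The variables are "stratification variables: diagnosis, municipality, employment status; age; gender; time to stable RTW", followed by "psychometric variables at baseline and all follow-up at outcome time: BDI, BAI, WSAS and PSS". Section 6.8.3.7 repeats the same list for outcomes 4-7 and 16-48. Neither section adds the scale being imputed, and neither names randomised arm.

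The analysis model is richer. Section 6.8.3.2 specifies "Linear mixed-effects model with unstructured covariance", with pairwise arm differences taken from its marginal means. Section 6.8.3.1 gives the data that enter it: "All 6-month follow-up outcome analyses are calculating using baseline and 6-month follow-up observations", and at the last visit "All 24-month follow-up outcome analyses are calculating using baseline and 6-, 12-, and 24-month follow-up observations".

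**The concern.** An imputation model should contain at least the variables in the analysis it feeds. Here the analysis of, say, 12-month KES uses arm and the participant's earlier KES scores, while the imputation of a missing 12-month KES is given neither.

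Missing at random has to hold given the variables actually used. For an unlisted scale, the list makes that assumption harder to satisfy than the collected data require: dropout must not depend on the scale's own earlier score once the listed variables are known. If a participant misses a whole visit, the listed scales are absent there too, and the best remaining predictor is the one left out.

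At stake are the arm differences on 24 exploratory outcomes. The missing arm term reaches further, because it concerns every questionnaire outcome that uses the list, including secondary outcomes 4-7.

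**Working it through.** The plan states no figure on this point, so there is none to reproduce.

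**Count, from the outcome table in 6.4.** Unlisted scales with outcomes at all three visits:
- 4DSQ (16-18)
- KES (27-29)
- EQ-5D-5L (30-32)
- QOLS (33-35)
- IPQ personal control (36-38)
- RTW-SE (39-41)
- GSS (42-44)
- SPS (46-48)

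That is 8 scales x 3 visits = 24 outcomes, all exploratory. CSQ-8 (45) is measured at 6 months only, so it has no earlier score to add.

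**Simulation A: the visit is missed and only baselines remain.** The 198 per arm comes from SAP 3.3. Everything else is assumed, because the SAP gives no correlations or missingness rates:
- own baseline to own follow-up correlation 0.6
- own baseline to listed-scale baseline 0.6
- listed-scale baseline to own follow-up 0.4
- true arm difference -0.30 SD
- 41% missing in one arm and 27% in the other, with the log-odds of missingness rising by 1 per SD of own baseline

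Missing values are drawn from a normal regression with parameter uncertainty. The analysis regresses follow-up on arm and own baseline.

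| Imputation model | Estimate (truth -0.30) |
|---|---|
| Listed scale only, as written | -0.17 |
| Listed scale + arm | -0.26 |
| Listed scale + own score, no arm | -0.19 |
| Listed scale + own score + arm | -0.30 |

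Own-score omission alone: (0.30 - 0.26)/0.30 = about 13% too small. With equal missingness and arm included, the estimates are -0.302 without the own score and -0.301 with it. Their standard deviations are 0.102 and 0.099, a ratio of 1.03.

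The no-arm result can be checked by hand. Without arm, imputed values follow one regression for both arms and carry almost no arm difference, so the effect shrinks roughly by the observed share. Average missingness is (41 + 27)/2 = 34%, and -0.30 x (1 - 0.34) = -0.198, close to the simulated -0.19. This shrinkage does not need missingness to differ between arms.

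**Simulation B: listed scale fully observed at every visit, which favours the plan.** 198 per arm; three visits; within-scale correlation 0.65; between-scale 0.3 to 0.5; 35-40% missing at 12 months.

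| Dropout mechanism | True effect | List | List + arm | List + own + arm |
|---|---|---|---|---|
| Completely at random, or on the listed scale | 0.3 | 0.23 to 0.26 | 0.30 to 0.32 | 0.30 to 0.32 |
| On own 6-month score, same direction in both arms | 0.3 | 0.21 to 0.24 | 0.27 to 0.29 | 0.29 to 0.30 |
| On own earlier score, opposite directions by arm | 0 | -0.10 to -0.19 | -0.17 to -0.31 | about 0 |

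The second row shows a small bias even with one common dropout rule, because the treatment effect shifts the 6-month score and so makes missingness differ between arms. The third row is a deliberately extreme mechanism. It shows that adding arm alone does not cure dropout that depends on own scores differently by arm.

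**The case against.** The strongest reply is that the list names auxiliary variables, and that the scale's own repeated scores and arm are taken for granted as part of the analysis model. An analyst might well work that way. But both sections introduce the variables as those to be used, and the list does include baseline and follow-up scores for four scales, so the text does not convey that reading. If it was intended, one sentence settles the matter.

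Three further points stand and limit the concern:
- The baseline table in 5.2 names only BDI, BAI, WSAS and PSS. Baselines for the other scales are inferred from the general wording of 6.8.3.1, which also covers CSQ-8, a treatment-satisfaction scale with no plausible baseline. A baseline SPS is also doubtful, since participants are on sick leave at randomisation. Even so, for 12- and 24-month outcomes the earlier follow-up scores exist and are not listed.
- The simulations simplify. A uses one listed scale and one follow-up, where the plan has four listed scales, time to stable RTW and a repeated-measures model. With four baseline proxies and arm included, the estimate moved only from -0.26 to -0.27.
- Section 6.2.1 plans a replacement analysis at the mean plus or minus 2 SD that does not depend on this imputation model, and missingness is reported by arm. Neither repairs the main analysis.

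A reader might infer that the secondary questionnaire outcomes also lose their own history. They do not: BDI, BAI, PSS and WSAS are on the list. For them only the missing arm term matters.

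**Conclusion.** The point holds as a conditional weakness in the imputation specification. Read as written, the list gives eight exploratory scales an imputation model without their own earlier scores, and gives all questionnaire outcomes one without randomised arm.

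With arm included, leaving out own scores biases the arm difference only if dropout depends on those scores and differs between arms: about -0.26 for a true -0.30 in the base case, and more under extreme mechanisms. The direction depends on which arm loses which participants. Leaving out arm is the larger and less conditional problem, pulling a true -0.30 to about -0.17 to -0.19 at roughly one third missing.

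It would go too far to infer that the trial's questionnaire results are biased by these amounts. The SAP gives no missingness rates or correlations, does not say that dropout depends on earlier scores, and may have been meant to include the omitted variables. The primary outcome is register-based and untouched. This is a low-priority but cheap correction.

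**What to change.** In 6.7.2 and 6.8.3.7, state that the imputation model for each questionnaire outcome includes that scale's own score at baseline (where collected) and at every visit up to the outcome time, plus randomised arm, and that the variables now listed are kept as auxiliaries. Both additions are needed: own scores without arm still give about -0.19 for a true -0.30, and arm without own scores about -0.26.

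The cost is one sentence in each section and a re-run of the imputation on variables already collected. The downside is a somewhat larger imputation model, run separately for each scale.

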6.8 ANALYSIS METHODS PER OUTCOME GROUP

This section describes the details of the statistical analyses. Since several outcomes require exact same analysis methods, outcomes are grouped for the following description

6.8.1 TIME TO RETURN TO WORK-OUTCOMES (OUTCOMES #1, #3 AND #8)

This section describes primary outcome *Time from baseline to RTW* at 12-month follow-up (1), and the secondary outcomes *Time from baseline to RTW* at 6- (outcome 3) and 24-month follow-up (outcome 8). The 24-month follow-up outcome will be calculated no earlier than June 2020. The other two, readily after the publication of this SAP, but before unblinding of analysts.

6.8.1.1 CALCULATION OF THE OUTCOME: SPECIFIC MEASUREMENT AND UNITS (AND TRANSFORMATION, WHERE APPLICABLE)

Time from baseline to RTW is defined as the number of weeks from randomization date, to stable return to work. Stable return to work is defined as 4 weeks consecutively in work, i.e. with no sick leave benefit those 4 weeks in the Dream register, and a so-called “branch code” in at least some of this 4 week period (benefit codes are week-based, branch codes are month based, and hence a period of 4 weeks may represent only one month, or overlap a two month period; in the latter case, return to work will be attained if at least one of these registrations contains a branch code; a branch code means that the individual received salary from an employer in this period). Time of event is first day of the four weeks.

These events will define censoring: 1) moving out of the country, 2) death, 3) public retirement pension (Da.: “Folkepension”), and 4) voluntary early retirement scheme (Danish: “Efterløn”).

At randomization all participants are, according to inclusion criteria, on sick-leave from employment or vacancy. Some participants might be on sick-leave from an employment in a *flexjob*⁷, and hence receiving *flexjob benefit* during employment. This benefit is changed to *flexjob sick-leave benefit* similar to regular sick leave benefit for participants not granted flexjob benefit prior to randomization. In these cases (of participants granted flexjob benefit prior to randomization) RTW is defined as either not receiving flexjob sick-leave benefit for four consecutive weeks, along with a registered branch code as above mentioned (or alternatively not receiving flexjob benefit, but an ordinary salary indicated by a branch code during those four weeks).

⁷ “Flexjob” is one of the Danish benefit schemes; it is a subsidy granted those with a chronic reduced work capacity

For participants, who at baseline are on sick-leave from vacancy (but not receiving flexjob benefit), RTW can both be defined as above mentioned (four consecutive weeks without sick leave benefits and a branch code during those four weeks) or receiving flexjob benefit for four consecutive weeks and a branch code during those four weeks.

6.8.1.2 SPECIFIC ANALYSIS METHOD AND RESULT PRESENTATION

Comparisons of RTW time will be calculated as hazard rate ratios between groups (and corresponding 98,3%CI), using a Cox-regression model.

Kaplan-Meier curves will be presented to illustrate the cumulative incidence of first stable return to work event in each trial-arm.

6.8.1.3 COVARIATE ADJUSTMENT

Only for stratification variables, see 6.1 “Covariate adjustment in general”.

6.8.1.4 STATISTICAL METHOD ASSUMPTION CONTROL

Assumptions for the proportional hazards (~Cox-) regression model are proportional hazards; this will be controlled performing af Schoenfeld (SF) test for residuals and visual inspection.

6.8.1.5 ALTERNATIVE ANALYSIS METHOD IN CASE OF ASSUMPTION FAIL

If the SF test is positive ($p < 0,05$), the analysis will we performed adjusted for the interaction between time and treatment group allocation. If SF test hereafter is still positive, the analysis will instead be adjusted for the interaction between *quadratic* time (time²) and treatment group allocation. If SF test hereafter is still positive, the analysis will instead be adjusted for the interaction between *log*(time) and treatment group allocation. If SF test hereafter is still positive, the analysis with the highest p-value will be reported.

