3.3 SAMPLE SIZE

Replicated from protocol follows:

³ <https://www.psykiatri-regionh.dk/Kvalitet-og-udvikling/udvikling/ibbis/Sider/IBBIS-forskning.aspx>

The sample size is based on a sample size calculation, using the 'Power and Sample Size' calculation programme⁴.

Type I error (α) risk

In each of the two RCTs we wish to conduct multiple comparisons (between 3 groups), and hence significance level must be as follows, due to Bonferroni correction:

$$\alpha = \frac{0,05}{3} = \frac{1}{60} = 0,0167$$

Type II error (β) risk

The organizational constellation of the interventions has not yet been trialled, and thus the desired power shall be set to:

$$\beta = 0,9$$

If it turns out that we cannot include enough participants, the power could be set to: $\beta = 0,8$

Hazard ratio (R)

The mean difference in time for return to work will be calculated as a hazard ratio. We estimate that as sufficient HR is

$$R = 1,5$$

since just 50 % faster return to work time in the intervention groups will convey a relevant economic benefit, due to the hence smaller loss of productivity.

Mean time to return to work (M_1)

Number of days from baseline to return to work is conservatively estimated to be 210 days, after an observed range from 104 to 210 days, in the control groups in three Dutch RCTs⁵⁻⁷, which were comparable to the control groups in the IBBIS RCTs.

Hence,

$$M_1 = 210$$

Inclusion time period (A)

We will include participants through 24 months,

$$A = 730[\text{days}]$$

Ratio between groups (m)

Ratio is 1:1:1, and hence $m = 1$

Follow-up time (F)

We will follow participants up for 365 days, in which they will contribute with risk time in the survival analysis, hence $F = 365$

Result

In each group, due to the above-mentioned variables, we need

198 participants per group, and with three groups that yields a need for, with power = 0.9,

⁴ <http://ps-power-and-sample-size-calculation.software.informer.com>

$$N = 198 \frac{\text{participants}}{\text{group}} \times 3 \frac{\text{groups}}{\text{trial}} = 594 \text{ participants}$$

If, in case of insufficient inclusion possibilities, power could be lowered to 0.8. In such case we would need the following number:

$$N = 153 \frac{\text{participants}}{\text{group}} \times 3 \frac{\text{groups}}{\text{trial}} = 459 \text{ participants}$$

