4 STATISTICAL PRINCIPLES

4.1 CONFIDENCE INTERVALS AND P-VALUES

For all outcomes, the three randomization groups are pairwise compared. Due to these multiple comparisons, we will calculate 98,3% confidence intervals, according to Bonferroni correction of desired α -level of 0,05 in testing of 3 hypotheses:

$$\alpha\text{-level: } 0,05 \times \frac{1}{3} \cong 0,0167 \Rightarrow \text{Confidence Interval: } 1 - 0,0167 \cong 98,33\%$$

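### The fallback for non-proportional hazards in time to return to work does not fix which hazard ratio or test compares each pair of arms; this is still open for the 24-month outcome #8

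*SAP*

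**What the plan says.** SAP 6.8.1 covers time to first stable RTW at 12 months (#1, primary), 6 months (#3) and 24 months (#8), the last two secondary. The effect measure is set in 6.8.1.2: "Comparisons of RTW time will be calculated as hazard rate ratios between groups", with 98.3% confidence intervals from a Cox model. Section 4.1 adds that "For all outcomes, the three randomization groups are pairwise compared". The sample size in 3.3 rests on a single ratio of 1.5: "The mean difference in time for return to work will be calculated as a hazard ratio".

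On proportional hazards, 6.8.1.4 says "this will be controlled performing af Schoenfeld (SF) test for residuals and visual inspection". It does not say whether the test is global or for the arm term, or on which time scale. If it is positive at 0.05, 6.8.1.5 states that "the analysis will we performed adjusted for the interaction between time and treatment group allocation". If it stays positive, arm × time² replaces that term, and then arm × log(time). If it is still positive, "the analysis with the highest p-value will be reported". Which p-value is meant is not stated; I read it as that of the Schoenfeld test.

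On timing, 1.2 shows that version 2 was written after the 6- and 12-month analyses and before those at 24 months. Section 6.8.1 says "The 24-month follow-up outcome will be calculated no earlier than June 2020", and 3.5 says that all 24-month analyses are unblinded.

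**The concern.** The text treats the interaction as an adjustment, as if the arm coefficient kept its meaning. It does not. With arm × time in the model, each pair has a curve of hazard ratios, and the single ratio promised in 6.8.1.2 no longer exists. Section 4.1 names the pairs, but no section says at which week, or by which coefficient, average or joint test, a pair is then compared. The form of the interaction is also picked by repeated tests on the same data.

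For #8 that choice would be made with allocation known. One fitted model can give a ratio near 1 or well above 1, and a significant or non-significant result, depending on the reading. The Kaplan–Meier display in 6.8.1.2 ("Kaplan-Meier curves will be presented to illustrate the cumulative incidence") lets a reader see crossing or late separation, but it does not fix which number, interval or p-value is reported.

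**Working it through.** **1. The plan's own figure.** Inputs from 3.3: α = 0.05/3 = 1/60 (taken as two-sided), power 0.9, ratio 1.5, control time 210 days, accrual 730 days, further follow-up 365 days. With exponential times and medians of 210 and 315 days, the event probabilities are 0.887 and 0.777.

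n per group = (z₁₋α/₂ + z_power)² / (ln 1.5)² × (1/p₁ + 1/p₂) = (2.394 + 1.282)² / 0.1644 × (1/0.887 + 1/0.777) ≈ 198.4

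The SAP has 198. Power 0.8 gives 153.8 against the SAP's 153. The design is therefore built on one constant ratio.

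**2. What the arm coefficient becomes.**
- Arm × time: ln HR(t) = b + c·t, so exp(b) is the ratio at t = 0, that is, at randomisation.
- Arm × time²: likewise the ratio at t = 0.
- Arm × log(time): ln HR(t) = b + c·ln t, so exp(b) is the ratio at one time unit. Going from weeks to days changes b to b − c·ln 7. Section 6.8.1.1 measures the outcome in weeks while 3.3 works in days; either way the reference point is arbitrary.

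**3. Simulation of one pair.** There were 198 per arm, a control median of 210/7 = 30 weeks, 104 weeks of follow-up, two-sided α = 1/60, no dropout and no covariates. The Schoenfeld test was a score test for arm × t at 0.05, with arm × time as the fallback. Ratios above 1 mean faster RTW. There were 20,000 replicates for (a) and 5,000 each for (b) to (d). The effect paths in (c) and (d) are my assumptions: (c) is 1.0 to week 18, then 1.8; (d) is 1.2, then 1.7.

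| Result reported | (a) No effect: false positives | (b) Constant 1.5: power | (c) 1.0 then 1.8: power | (d) 1.2 then 1.7: power |
|---|---|---|---|---|
| Plain Cox, no fallback | 1.7% | 93.2% | 88% | 92% |
| Rule, arm coefficient | 2.7% | 90.7% | 45% | 70% |
| Rule, HR at week 26 | 1.8% | – | 82% | – |
| Rule, HR at week 52 | 2.1% | – | 94% | 94% |
| Rule, HR at week 104 | 3.1% | – | 94% | 94% |
| Rule, joint 2-df test | 2.5% | 93.6% | 93% | 94% |
| Rule, any reading counts | 4.0% | – | – | – |
| Fallback used | 5% (nominal) | 5% | 49% | 24% |

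False-positive rates are two-sided. Power is for a Wald test in the direction of benefit, except the joint test, which has no direction. In (c) plain Cox gives 1.45, while the arm × time model gives 1.13, 1.40, 1.75 and 2.73 at weeks 0, 26, 52 and 104.

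**4. Sensitivity.**
- If the 210 days are a mean, the control median is 30 × ln 2 = 20.8 weeks. Then (a) gives 1.5% for Cox, 2.5% for the arm coefficient, 3.2% at week 104 and up to 4.1% for any reading. Case (c) gives 73% for Cox, 31% for the arm coefficient, 89% at week 52 and 87% for the joint test.
- With three arms and a 2-df Schoenfeld test (4,000 replicates), the fallback is used in 5% of trials with no effect or a constant 1.5. It is used in 41–54% when group 3 follows path (c), depending on group 2.
- Under an assumed crossing path (0.75 to week 20, then 1.3), one arm × time model gives 0.86 at week 0 and 1.64 at week 104. Fitting it in all of 1,000 runs, the arm coefficient is significant for slower RTW in 10%, and the week-104 ratio is significant for faster RTW in 31%. The reading can reverse the direction of the conclusion.

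**The case against.** **The large figures rest on assumed paths.** This is true. The SAP states no hazard path and reports no Schoenfeld result. Section 1.2 says that the usual-care arm tended to return fastest by 6 months. Its explanation, however, concerns recurrent sick leave, which cannot alter time to first stable RTW, so it does not show non-proportional hazards for #8.

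**Under the plan's own assumption little is lost.** Also true: at a constant 1.5 the fallback is used in about 5% of trials and costs at most 2–3 points. With no effect, the week-26 reading is about nominal. The 4.0% is a worst case of selective reporting.

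**The later steps may never be reached.** If the Schoenfeld test uses linear time, its score is zero once arm × time is fitted, so the squared, log and highest-p-value steps do nothing. With a log- or rank-time test, a check of case (c) was still positive after arm × time in 12% and 22% of trials. The effect of those later steps was not simulated, so the figures above do not measure them.

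**A literal reader would report the arm coefficient.** Perhaps, but that does not rescue the rule. That reading gives 2.7% false positives and 45% power in case (c).

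**The remedy also reacts to the Schoenfeld test.** It does, but the main result no longer depends on that test, and the added contrast is named in advance.

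**Conclusion.** The concern holds. When the fallback is triggered, 6.8.1.5 replaces the promised single ratio with a curve, and nothing in the SAP says how a pair of arms is then compared. It should be fixed before the unblinded analysis of #8.

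The gap itself follows from the text and needs no simulation. Its size depends on assumptions. It is small under a constant ratio of 1.5. With no effect the excess in false positives is modest, unless the reading is chosen after seeing results. It is large under a delayed effect, where both the reported ratio and the power are set by the reading. All sizes assume 198 per arm, no dropout, no covariates and an arm-only test on linear time. For #1 and #3 any change would now be post hoc.

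**What to change.** For #8, before the unblinded analysis:
- Delete the sequence of interaction terms and the highest-p-value rule from 6.8.1.5.
- Always report the plain Cox hazard ratio and its test as the main result for each pair.
- State that the Schoenfeld test applies to the arm term, and on which time scale.
- If it is positive, add one prespecified pairwise contrast with a 98.3% interval: the difference in restricted mean weeks to RTW up to week 104. Hazard ratios at weeks named now would be an alternative. Adjust the contrast for the stratification variables, as 6.1 already requires.

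For #1 and #3, show the plain Cox result beside any fallback result, labelled post hoc.

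With no effect, the proposed rule gives 1.8% false positives per pair even if either result is counted (12,000 replicates). The cost is SAP wording and a few lines of code for #8, and one extra reported line for #1 and #3; no new data are needed.

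There are two downsides. Under non-proportional hazards the Cox ratio is a time-averaged value. The restricted mean is also less sensitive to late effects than Cox: power is 81% against 88% in case (c), or 68% against 73% if 210 days is a mean. In case (b) both have 93%.
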